6.2. Overall Study Design

The trial design is shown in [Table 3](#) and the study events schedule is shown in [Table 4](#) and detailed in this section. This Version 6.0 amendment prioritizes vaccination of Groups 1 and 3, to meet the time limitations of the research contract. The new study design requires a modification to the randomization approach presented in Version 4.0. That version accommodated a change in the timing of new TDS-ID device manufacture; however, due to the impact of the COVID-19 pandemic on the timing of this overall study, and the timing of TDS-ID device manufacture is no longer a concern because that has been completed, the Version 4.0 randomization approach is no longer applicable and is considered suboptimal. The Version 6.0 randomization approach is presented in below and [Appendix B](#).

The study design, including doses and schedule, is based on the experience of a team of investigators to include personnel at USAMRDC ORA, USAMRIID, and Ichor who have performed clinical trials with similar DNA vaccine constructs using Ichor's TDS-IM V1.0 EP device for DNA vaccinations. These TDS-IM V1.0 and TDS-ID EP devices have been tested in humans previously in a recent clinical trial to evaluate the safety and immunogenicity of a DNA vaccine for Venezuelan encephalitis virus ([Hannaman et al, 2016](#)). These same codon-optimized HTNV and PUUV DNA vaccine products have also been tested in humans previously, albeit only using the TDS-IM V1.0 EP device, and at lower dose levels than proposed in this study. Previous studies examined these vaccines in Phase 1 ([Hooper et al, 2014](#)) and 2a clinical trials at up to 2-mg dose levels per IM EP administration, whereas this study is testing up to 6 mg of DNA per administration using the 2 devices. The GLP repeat-dose rabbit toxicology and immunogenicity study performed in support of this study administered these same codon-optimized HTNV and PUUV DNA vaccines at up to 6 mg doses using the 2 devices and at an increased dosing frequency compared to this proposed Phase 1 clinical trial design. The rabbit toxicology study did not reveal safety concerns for the use of this higher dose level and with these 2 devices.

This study will be a single-center, randomized, study of the HTNV, PUUV, and combined HTNV/PUUV DNA vaccines delivered IM and ID by EP.

The study may enroll 6 randomized groups of 12 subjects each for a total of 82 subjects (This accounts for 10 replacement subjects for Group 6, impacted by COVID). The study had initially planned to enroll 6 randomized groups of 12 subjects each, for a total of 72 subjects. Ten subjects in Cohort 6 may be replaced because vaccination and data collection were negatively impacted in this group by COVID-19 pandemic quarantine restrictions. This approach will ensure at least 60 subjects complete all vaccinations at around 10 subjects per group, taking possible attrition into account. Subjects will receive one dose of vaccine on each of Days 0, 28, and 56 and will be followed until Day 220.

The HTNV and PUUV DNA vaccines will be administered to subjects as follows:

Group 1⁴: 0.6 mg HTNV by ID EP

⁴ Sentinel subjects will not be included for Groups 1 and 3 because the dose is lower than the 2.0 mg/mL dose that was previously evaluated for these products.

Group 2: 3.0 mg HTNV by IM EP

Group 3: 0.6 mg PUUV by ID EP

Group 4: 3.0 mg PUUV by IM EP

Group 5: 1.2 mg HTNV/PUUV by ID EP

Group 6: 6.0 mg HTNV/PUUV by IM EP

Every subject will receive 1 injection on Days 0, 28, and 56 for a total of 3 injections.

The first study enrollment activities will involve selection and randomization of volunteers as sentinels for Groups 2 and 4, and then subjects for the remainder of the Group 2 and 4 cohort. The sentinel subjects for Groups 2 and 4 (n = 2 per group, or 4 total) will be vaccinated and evaluated for 48 hours prior to dosing the remainder of Group 2 and 4 (n = 10 per group, or 20 total). After the first dose for all subjects in Groups 2 and 4 has been successfully completed and none of the halting criteria are met, then the first dose will be given to 2 sentinel subjects in Group 6 (n=2 , total of 2 subjects) on the same day, and those 2 subjects will be followed for 48 hours as per the Sentinel Group Halting Rules. The SRC will meet and evaluate the safety data collected in the 48-hour period post-vaccination for sentinels in Group 6. If the SRC finds that the halting rules have been met (Section 6.6.1.1), the PI will notify ORA PSSO within 24 hours. An SMC meeting will be held to conduct a review of clinical and laboratory safety and reactogenicity data. After the meeting, the SMC will make its recommendations in writing regarding continuation, modification, or termination of the clinical trial. If the recommendation is to proceed, enrollment, randomization, and vaccination (Day 0) of the remaining volunteers in Group 6 (n=10 per group). The first dose will be given to 2 sentinel subjects in Group 5 (n=2, total of 2 subjects) on the same day and those 2 subjects will be followed for 48 hours as per the Sentinel Group Halting Rules. The SRC will meet and evaluate the safety data collected in the 48-hour period post vaccination for sentinels in Group 5. If the SRC finds that the halting rules have been met (Section 6.6.1.1) the PI will notify ORA PSSO within 24 hours. A SMC meeting will be held to conduct a review of clinical and laboratory safety and reactogenicity data. After the meeting, the SMC will make its recommendations in writing regarding continuation, modification, or termination of the clinical trial. If the recommendation is to proceed, enrollment, randomization, and vaccination (Day 0) of the subjects in Groups 1 and 3 (n=12 per group, total of 24 subjects) will commence. Subjects in Groups 1 and 3 will be evaluated for the 48-hours post-vaccination for any halting criteria on the Day 2 clinic visit (Table 4). After completion of enrollment and first vaccination for Groups 1 and 3, the remaining subjects for Group 5 and ten Group 6 replacements (total of 20 subjects) may be enrolled, randomized and vaccinated (Day 0), provided that the enrollment of these 20 subjects can be completed within 4 months (see randomization schedule in Appendix B). Subjects are expected to complete a total of 11 visits (not including screening). There will be a 6 month follow-up after the final injection (Day 220). Overall study duration is expected to be approximately 8 months.

Table 4: Study Events Schedule

Study Visit	Screen 1	Screen 2	1	2	3	4	5	6	7	8	9	10	11	12
Study Month	-3.2		0	0.1	0.5	1.0	1.1	1.5	2.0	2.1	2.5	3.0	5.0	8.0
Study Day	-90 to -7^a		0	2	14	28	30	42	56	58	70	84	140^{b,c}	220
Visit Window (Days)				+ 1	± 2	± 4	± 1	± 2	± 4	± 1	± 2	± 4	± 7	± 14
Obtain Informed Consent and Demographics	X													
Administration Procedure ^b			X				X			X				
Review Eligibility ^c	X	X ⁿ	X				X			X				
Medical History	X	X ⁿ	X	X	X	X	X	X	X	X	X	X	X	X
Concomitant Medications	X	X ⁿ	X	X	X	X	X	X	X	X	X	X	X	X
Adverse Event Assessment			X	X	X	X	X	X	X	X	X	X	X	X ^o
Physical Examination ^d	X	X ⁿ	X	X	X	X	X	X	X	X	X	X	X	
Skinfold Thickness Measurement of All Possible Injection Sites and Weight	X	X ⁿ	X			X			X					
Reactogenicity Assessment ^e			X	X	X	X	X	X	X	X	X	X	X	X
Collection of Written Memory Aids from Subjects					X			X			X			
Vital Signs ^f	X	X ⁿ	X	X	X	X	X	X	X	X	X	X	X	X
Clinical Safety Laboratory Testing ^g	X	X ^{a,n}	X ^h		X	X ^h		X	X ^h		X			
Serum Pregnancy Test (B-HCG)	X													X
Urine B-HCG		X ⁿ	X			X			X					
HIV, HCV, HBsAg	X													
Pre-screening (PsVNA50) ⁱ		X												
Blood for Humoral Immune Response to Vaccination ^j			X			X			X			X	X	

Study Visit	Screen 1	Screen 2	1	2	3	4	5	6	7	8	9	10	11	12
Blood for Future Use Immunogenicity ^j			X			X			X			X	X	
Electrocardiogram (ECG) ^k	X													X
HLA Testing (buccal swab)			X											
Total Blood Sample Volume (mL)	33	34.5	22.5	0	12.5	22.5	0	12.5	22.5	0	12.5	72.5	23.5	0°

^a All subject screen visit procedures will be performed on the first screening visit (Screen 1) to include clinical safety lab tests. The immunogenicity tests will be performed at a secondary screening visit (Screen 2) allowing sufficient time to process the sera while assuring subjects' safety lab values are still within accepted values within 56 days prior to first dose administration.

- Days calculated based on 28-day months.
- For subjects who withdraw prior to completion of all study visits, the subject is requested to return as soon as possible to the date of termination for completion of termination procedures detailed in Section 8.1.5 for final safety and immunogenicity assessments.

^b Administration procedures will include a post-injection observation period/reactogenicity assessment at least 30 minutes after vaccine administration. Vital signs will also be rechecked.

^c Safety lab results will not be reviewed prior to product administration, and inclusion/exclusion criteria will be applied, with the exception of exclusion criteria 9, which will not be applied for vaccinations 2 and 3 because it is for screening prior to enrollment.

^d Physical examination will be completed at screening visit 1, and includes examination of general appearance, skin, neck (including thyroid), eyes, nose, throat, lungs, heart, abdomen, lymph nodes, extremities, and a basic neurological assessment; directed physical exams will be completed at all other visits. A directed physical exam is defined as a focus, complaint-driven physical examination. In the absence of a complaint, a physical exam will not be performed.

^e Reactogenicity assessments will include subject completion of a memory aid each day for 14 days after a vaccination visit.

^f Vital sign measurements include oral temperature, heart rate, respiratory rate, and systolic and diastolic blood pressure.

^g Complete blood count (CBC [WBC, Hb, platelets] with differential), glucose, creatinine, AST, ALT, total bilirubin. Lab abnormalities will be followed up on an ad hoc basis as per the study investigators. At Screen 1, a collection of 2.7 mL blood will be used to perform the PT/PTT tests to determine any coagulation abnormalities for exclusion criterion 25.

^h Blood will be drawn prior to study product administration. Safety lab results will not be reviewed prior to product administration.

ⁱ Approximately 10 mL of blood will be collected at Screen 2 to determine subject eligibility.

^j Blood collected for the humoral immune response to vaccination will be approximately 10 mL on Days 0, 28, 56 and 140; any remaining blood will be stored for future use. Approximately 50 mL of blood will be collected on Day 84 for humoral immune response to vaccination and for future use.

For determination of any cardiac abnormalities, an ECG will be performed at Screen 1 and study visit 11.

ⁿ Procedures will be completed only if Screen Visit 2 falls outside of the 56-day screening window prior to vaccination. See Section 8.1.2 for further clarification

^o Scripted telephone contact for collection of Serious Adverse Event information

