- 1. History of prior infection with any hantavirus virus or prior participation in an HTNV, PUUV, or Andes virus vaccine trial
- 2. Has plans to travel to an area with endemic^e Hantaan, Puumala, Seoul, and Dobrava virus transmission during the study
- 3. History of severe local or systemic reactions to any vaccine or vaccine products^f or a history of severe allergic reactions
- 4. Is currently participating in or plans to participate in another study involving any investigational product (eg, vaccine, drug, or biologics) or a study that involves blood drawing, and/or an invasive procedure^g
- 5. Receipt or planned receipt of any live vaccination, experimental or otherwise, within the period 30 days prior to or after each vaccination and receipt or planned receipt of an inactivated vaccination, experimental or otherwise, within the period of 14 days prior to or after each vaccination
- 6. Individuals, who based on clinical assessment by the investigator, have insufficient muscle mass to accommodate the 1 inch/25 mm penetration depth or have a skinfold thickness at eligible injection sites (deltoid region) that exceeds 40 mm
- 7. Individuals in whom the ability to observe local reactions at the eligible injection sites (deltoid region) is, in the opinion of the investigator, unacceptably obscured due to a physical condition or permanent body art
- 8. Presence of any surgical or traumatic metal implants at the injection site (medial deltoid muscles or overlying skin)
- 9. Subjects with autoimmune disorders or chronic inflammatory disorders with a potential autoimmune correlation
- 10. Receipt of immunoglobulins and/or any blood products within the 120 days preceding screening or planned administration during the study period
- 11. Donation of blood to a blood bank within 56 days prior to screening and at any time during the study period
- 12. Subject seropositive for hepatitis B surface antigen (HBsAg) or hepatitis C antibodies (anti-HCV)

13. Any confirmed or suspected immunosuppressive or immunodeficient condition, including HIV infection, or use of anticancer chemotherapy or radiation therapy (cytotoxic) in the 3 years prior to screening

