⁷ Women of childbearing potential are defined as those who have not been sterilized via tubal ligation, bilateral oophorectomy, bilateral salpingectomy, hysterectomy, or successful Essure® placement (permanent, non-surgical, non-hormonal sterilization) with history of documented radiological confirmation test at least 90 days after the procedure (or with use of another birth control method if history of confirmation test not confirmed), still menstruating or < 1 year of the last menses if menopausal. For this study, an effective contraceptive method is defined as one that results in a failure rate of less than 1% per year when it is used consistently and correctly.

9. Negative hantavirus PsVNA test result at screening.

10. Screening laboratory test values:

- Hemoglobin > 11.0 g/dL for women; > 12.9 g/dL for men
- WBC with differential and platelets either within the normal range (provided by the laboratory performing the analysis) or a Grade 1 deviation from normal (per [Appendix C](#)) and deemed clinically insignificant
- Alanine aminotransferase (ALT), aspartate aminotransferase (AST) and bilirubin < 1.1x upper limit of normal (ULN) (per the normal range provided by the laboratory performing the analysis)
- Serum creatinine < 1.35 g/dL

For all other screening laboratory test values, results that do not meet the definition of a Grade 1-4 value within 56 days prior to enrollment (see [Appendix C](#), “Clinical and Laboratory Toxicity Grading Scales”) are eligible for enrollment.

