7.4. Subject Exclusion Criteria

Subjects meeting any of the following criteria will be excluded from the study:

1. History of prior infection with any hantavirus virus or prior participation in an HTNV, PUUV, or Andes virus vaccine trial.
2. Has plans to travel to an area with endemic⁸ Hantaan, Puumala, Seoul, and Dobrava virus transmission during the study.
3. History of severe local or systemic reactions to any vaccine or vaccine product⁹ or a history of severe allergic reactions.
4. Is currently participating or plans to participate in another clinical study involving any investigational product (including vaccines) or involves blood drawing, and/or an invasive procedure.¹⁰
5. Receipt or planned receipt of any live vaccination, experimental or otherwise, within the period 30 days prior to or after each vaccination and receipt of an inactivated vaccination, experimental or otherwise, within the period of 14 days prior to or after each vaccination.

⁸ Refer to the MOP for information on areas with endemic Hantaan, Puumala, Seoul, and Dobrava virus transmission.

⁹ This includes a known allergy to an aminoglycoside (eg, gentamicin, tobramycin, neomycin, and streptomycin).

¹⁰ An invasive procedure includes endoscopy, bronchoscopy, or procedure requiring administration of IV contrast or removal of tissue.

6. Individuals, who based on clinical assessment by the investigator, have insufficient muscle mass to accommodate the 1 inch/25 mm penetration depth or have a skinfold thickness at eligible injection sites (deltoid region) that exceeds 40 mm.
7. Individuals in whom the ability to observe possible local reactions at the eligible injection sites (deltoid region) is, in the opinion of the investigator, unacceptably obscured due to a physical condition or permanent body art.
8. Presence of any surgical or traumatic metal implants at the site of administration (medial deltoid muscles or overlying skin).
9. Subjects with autoimmune disorders or chronic inflammatory disorders with a potential autoimmune correlation.
10. Receipt of immunoglobulins and/or any blood products within the 120 days preceding screening or planned administration during the study period.
11. Donation of blood to a blood bank within 56 days prior to screening and at any time during the study period.
12. Subject seropositive for hepatitis B surface antigen (HBsAg) or hepatitis C antibodies (anti-HCV).

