7.5. Termination of Dosing and/or Subject Withdrawal Criteria

Termination of dosing is defined as someone who elects to no longer receive doses but is willing to remain on the study for continued observations, immunogenicity assessment and monitoring of safety parameters. Withdrawal from study is defined as not participating in this study any longer, and not continuing to be observed by the study physician. Each subject may withdraw consent for continued dosing or from the study at any time without penalty. Counseling about the subject's health will be provided if he/she decides to discontinue participation in the study. Medical advice regarding what is in the best interest of the subject will be provided.

The PI may discontinue the subject's receipt of investigational product without the subject's consent if any of these criteria is met:

1. The discovery or development of any health condition within a subject that would make his or her continued participation in the protocol dangerous to him- or herself.
2. The failure of the subject to comply with the requirements of the protocol.
3. The scientific integrity of the study may be compromised by further participation.
4. Any significant finding that in the opinion of the investigator would increase the risk of the subject having an adverse outcome from further participation in the study.

For example:

- Pregnancy
- Receipt of disallowed licensed vaccine, experimental product or medication
- New onset of illness or condition that meets the Exclusion Criteria
- Medical condition or medication change for which continued participation, in the opinion of the site principal investigator or appropriate sub-investigator, would pose a risk to the subject or would likely confound interpretation of the results
- Presence of signs or symptoms that could confound or confuse assessment of study vaccine reactogenicity
- Grade 3 solicited or unsolicited adverse event that is ongoing, whether or not it is improved or resolving. An unresolved or continuing Grade 1 or Grade 2 adverse event is permissible following the documented determination by the site principal investigator or appropriate sub-investigator, that it would not render study vaccination unsafe or interfere with the evaluation of adverse events or immunologic response
- Grade 3 solicited or unsolicited adverse event that occurs without alternative etiology in the 7 days following study vaccination

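### Table 4 footnote c waives exclusion criterion 9 at doses 2 and 3 as a screening-only item, but criterion 9 in the current protocol is autoimmune or chronic inflammatory disease

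*Protocol*

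**What the plan says.** The Review Eligibility row of Table 4 (Protocol 6.2) carries footnote c. It first says that safety laboratory results are not reviewed before product is given. It then says the inclusion and exclusion criteria are applied, "with the exception of exclusion criteria 9, which will not be applied for vaccinations 2 and 3", and gives the reason: "because it is for screening prior to enrollment".

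Exclusion 9 is the same in both current protocol lists. The Synopsis has "9. Subjects with autoimmune disorders or chronic inflammatory disorders with a potential autoimmune correlation", and Section 7.4 has the same text under the same number.

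Footnote g of the same table says the PT/PTT sample at Screen 1 is taken "to determine any coagulation abnormalities for exclusion criterion 25". In Section 7.4, PT/PTT belongs to exclusion 24 (bleeding diathesis), and exclusion 25 is cardiac arrhythmia.

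Two other sections govern the later doses. Section 8.1.3 requires a review of eligibility and safety criteria before each vaccination and points to Section 7.5. Section 7.5 states: "The PI may discontinue the subject's receipt of investigational product without the subject's consent if any of these criteria is met". Its examples include "New onset of illness or condition that meets the Exclusion Criteria". Neither section makes an exception for exclusion 9.

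**The concern.** Footnote c is an operative instruction for a dosing visit. Taken at its word, it tells staff not to apply the autoimmune and chronic inflammatory exclusion before the second and third doses. The reason it gives does not fit: nothing in the Synopsis or Section 7.4 confines that exclusion to screening, and such a condition can appear between Day 0 and Day 56. The protocol therefore gives two answers on whether this criterion counts at doses 2 and 3.

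A second gap follows. If the waiver was meant for a laboratory criterion, it now points elsewhere, and the laboratory criterion (inclusion 10) is formally still to be applied at visits where footnotes c and h say the results are not looked at before dosing.

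**Working it through.** No power, alpha or sample-size figure is involved. The check compares the numbering across lists and then counts the visits the wording covers.

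**Step 1: do the footnote numbers fit the current lists?** The SAP's exclusion list (SAP 4.6) is bulleted, so its positions are found by counting. Its seventh bullet runs three criteria together (view of the injection site, metal implants, screening laboratory results). Split, these are items 7, 8 and 9.

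| Criterion | SAP 4.6, by count | Protocol Synopsis and 7.3/7.4 | Table 4 footnote |
|---|---|---|---|
| Metal implants | 8 | Exclusion 8 | – |
| Screening laboratory results | 9 | Inclusion 10 | – |
| Autoimmune or chronic inflammatory disorders | 10 | Exclusion 9 | c says 9 |
| Bleeding diathesis, PT/PTT | 25 | Exclusion 24 | g says 25 |

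Footnote g names its subject (PT/PTT), so its 25 is wrong against the current list by one place. Footnote c names no subject, only a reason. That reason does not fit current exclusion 9, but it does fit item 9 in the SAP order. Taking one item out of the exclusion list at position 9 moves every later item up by one, so 10 becomes 9 and 25 becomes 24. That single shift accounts for both footnotes.

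**Step 2: is another target possible?** Inclusion 9 is "Negative hantavirus PsVNA test result at screening", which also fits the stated reason. It would require footnote c to have named the wrong list, and it would not explain footnote g. It is the less likely reading, but the documents do not rule it out.

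**Step 3: what does the literal reading change at doses 2 and 3?**
- Footnote c: exclusion 9 is not applied.
- Section 7.4: exclusion 9 stands without qualification.
- Section 8.1.3: eligibility is reviewed before every vaccination, with no exception.
- Section 7.5: a new condition meeting the exclusion criteria is a ground on which dosing may be stopped, with no exception.
- Inclusion 10: not named in the waiver, although footnotes c and h say safety labs are not reviewed before dosing.

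**Step 4: how many dose-visits does the wording cover?**
- Whole trial: 82 subjects × 2 later doses = 164. This is a ceiling, because it assumes everyone receives doses 2 and 3.
- From the Version 6.0 restart: Appendix B counts 36 subjects already enrolled. Still to come are 2 Group 5 sentinels, 24 subjects in Groups 1 and 3, and up to 20 more in Groups 5 and 6. Check: 36 + 2 + 24 + 20 = 82.
- Section 6.2 makes the last 20 conditional on completing their enrollment within 4 months. Without them, 2 + 24 = 26 subjects; with them, 26 + 20 = 46.
- Later dose-visits if all are dosed: 26 × 2 = 52 to 46 × 2 = 92.

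**The case against.** The strongest reply is that this is a renumbering slip that signals itself. The footnote opens with safety labs and describes the waived item as a screening matter, so anyone who looks up exclusion 9 will see that it does not fit. A waiver of the autoimmune exclusion was very probably never intended. That stands as an account of how the error arose. It does not make the instruction correct, and the reader still has to guess which criterion is meant.

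A reader might infer that a subject with a new autoimmune disorder would simply pass the check at dose 2 or 3. The documents do not support that. Exclusion 20 (any medical condition the investigator judges a contraindication) still applies, as do exclusions 13 and 14 and the temporary exclusion for an evolving acute illness. Section 8.1.3 still requires an interim history and an eligibility review. What is lost is the specific criterion, and the decision falls back on judgment.

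A reader might also infer that the footnote overrides a mandatory stop. It does not: Section 7.5 says the investigator may discontinue dosing, and a footnote about an eligibility check does not remove that power. The conflict is between texts.

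On inclusion 10, it can be said that its wording concerns screening values and so limits itself. That softens the second gap but does not close it, because footnote c applies all criteria with one stated exception and inclusion 10 is not that exception.

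**Conclusion.** The point holds as an internal contradiction: footnote c is wrong as written, and footnote g's criterion number is also wrong. Read literally, footnote c removes the autoimmune and chronic inflammatory criterion from the eligibility check at doses 2 and 3, in conflict with Sections 7.4, 7.5 and 8.1.3, and leaves inclusion 10 unwaived. Investigator discretion remains as a backstop.

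The wording covers at most 164 dose-visits in all, and 52 to 92 from the Version 6.0 restart if all those subjects are dosed. It would be tempting to add Groups 1 and 3 to the remaining 20 subjects (24 + 20 = 44) and call 88 later dose-visits a minimum. That is not a floor, because the 20 are conditional, and it omits the two Group 5 sentinels. None of these counts measures risk: the relevant event is a disorder arising between Day 0 and about Day 56, and the documents give no rate for it.

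The mismatch with the current lists rests on the text alone. The explanation, that the footnotes kept their numbers when the laboratory criterion moved to the inclusion list, is an inference from the SAP's order, since the earlier protocol list is not among the documents.

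**What to change.** The sponsor should decide which criterion footnote c is meant to waive and reconcile footnotes c and g with Sections 7.3, 7.4, 7.5 and 8.1.3. Footnote c should name the waived criterion by its text as well as its number, and say whether inclusion 10 applies at doses 2 and 3, given that safety labs are not reviewed before dosing. The criterion number in footnote g should be corrected to match the PT/PTT item in Section 7.4. No view is offered on which clinical rule should apply.

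The cost is a few lines of footnote text in the next amendment. The correction of the references itself adds no visit, sample or analysis.
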